5.5 Lifestyle Considerations

5.5.1 Meals and Dietary Restrictions

No meals and dietary restrictions.

5.5.2 Caffeine, Alcohol, Tobacco, and Other Habits

There are no restrictions to the intake of caffeine, alcohol, or tobacco.

5.5.3 Physical Activity

Physical activity is restricted for the patients having an operation as follows: Rehabilitation consist of 5 weeks partial weight bearing, range of motion will be restricted for the first 3 weeks to 30 °flexion, 4th week 60 °, 5th week 90 °, then full range of motion exercises were allowed. Jogging is not allowed for 4 months and contact sport only after 6 months.

5.5.4 Other Activity

There are no restrictions to blood or tissue donation and sun exposure.

Driving is not allowed for operated patients for 8 weeks with manual transmission and when the right leg is concerned also for automatic transmission.

Heavy labour not for 3 months.

5.6 Screen Failures

Screen failures will be left in the study. The study will be performed after the principle: full analysis set. The principal investigator is performing the screening himself, thus screening failures will be limited.

6 TRIAL INTERVENTION AND CONCOMITANT THERAPY

6.1 Description of Trial Intervention

The investigator-initiated trial is a "low-intervention clinical trial" according to Article 2(3)CTR. It will be conducted in accordance with the "FSA-Kodex" and the joint recommendations of the BfArM and PEI on the planning, conduct and analysis of investigator-initiated trials. The clinical trial will be conducted in compliance with the protocol, with the CTR regulation and with the principles of good clinical practice according to Annex I section D 17 (a) CTR 536/2014.

The IMP is SUB184038, human cancellous bone, auxiliary medicinal product (NIMP) is Cephazolin, 2 gr. one shot just before surgery, IMP and NIMP for the surgical group only.

Fig. 2 example of packaging and labelling.

The IMP can be stored at room temperature (fig. 2). The transplant must be re-hydrated at least 30 min before implantation in physiological injectable solution (Fachinformation point 4.2).

Intervention for the surgery group: As for any surgical procedure, the patient receives an antibiotic shot (NIMP) just before surgery. The patient will be arthroscopically treated via the arthroscopic portal with implantation of a demineralized bone block (IMP: Spongioflex®, appropriate size (DIZG gGmbH, Berlin, Germany)) as a partial meniscus substitute. The block will be adapted to the defect size and secured with 2-4 inside-out sutures (Etidbond 0, Ethicon, Somerville, NJ). No dosing, the IMP has no systemic effect. The surgery (Intervention) will last between 60-90 minutes. The hospital stay is between 2-3 days after surgery. Follow-up visits: at the end of the hospital stay, after 6 weeks, after 6, 12 and 24 months and after 5 years for the operated group.

Non-operated group: no surgical treatment, no antibiotic shot, no visit at the end of the hospital stay, and no visit after 6 weeks. Follow-up visits after 6, 12 and 24 months and after 5 years.

Table 1: Trial interventions

| Trial intervention | Operated group | Non-operated group |
|--|----------------|--------------------|
| screening | yes | yes |
| enrollment | yes | yes |
| In-hospital surgery as summarized above with IMP and NIMP as defined above | yes | no |
| Follow-up includes MRI evaluation and IKDC, KOOS and VAS-pain-Score at each follow-up visit | yes | yes |
| at the end of hospital stay | yes | no |
| After 6 weeks | yes | no |
| After 6 months | yes | yes |
| After 12 months | yes | yes |
| After 24 months | yes | yes |
| ...After 5 years | yes | yes |

6.2 Rationale for Trial Intervention

Arthroscopy is an established method to treat meniscal lesions. This is the best way to protect the soft tissue and to minimize the risks for the patient. The IMP is a human cancellous bone block, which is hard when dry and has spongy soft properties when wet. It is sold in varied sizes. It can be sized in accordance with the defect size, it is pliable (important for shuttling through arthroscopic ports) and allows cell and fluid migration. The IMP has no systemic effect and thus does not have a dose. A case report [31] shows first promising results. The group around [name] [21] from the Charité has used Spongiflex® for rebuilding the glenoid surface and were unable to demonstrate re-ossification on subsequent MRI scans up to 12 months and could show successful restoration of the glenoid. There are still sufficient growth factors in the IMP to initiate cell migration from surrounding tissue. Demineralized bone, as Spongiflex®, supports soft-tissue ingrowth [20]. See 2.1 purpose of trial for more details.

There is no dose and no regime, thus there is no rational for dose and regime.

6.3 Dosing and Administration

The size of the IMP will be estimated by MRI evaluation and approved with the measuring rod during surgery by the operating surgeon.

The IMP will only be handled by the orthopedic surgeon. The patient does not handle the IMP and not the NIMP, thus no instructions for the patients are needed.

6.3.1 Trial Intervention Dose Modification

There is no dose, thus there is no dose modification

6.4 Treatment of Overdose

There is no dose, thus there is no overdose

6.5 Preparation, Handling, Storage and Accountability

6.5.1 Preparation of Trial Intervention

The preparation of the IMP is only handled by the investigator of the trial. The size of the IMP will be adapted

due to the defect size. The re-hydration of the IMP will be 30 min prior use in physiological injectable solution as explained in the “Fachinformation” (attached as separate document). The NIMP will be applied I.V.

6.5.2 Handling and Storage of Trial Intervention

The IMP can be stored at room temperature up to the date indicated on the package. Handling follows the instruction in the “Fachinformation” and as described under 6.2 and 6.5.1.

6.5.3 Accountability of Trial Intervention

The IMP and NIMP will only be handled by the investigator. Each patient does get only 1 IMP. Because the size will be adapted during surgery, he is able to order the IMP before knowing the patient's defect. He has a storage of the IMPs (in the operating tract) of the available sizes to treat several patients without the need to order. He orders via the hospital, where the treatment is performed from the manufacturer. The product is available on the market for orthopedic surgeons with a prescription.

There is no return of unused products, the rest of the IMP, which is not implanted, will be disposed in the operating tract. One IMP is only allowed to use for 1 patient, even the remaining part would be big enough for treating another patient (Fachinformation point 6.6).

6.6 Participant Assignment, Randomisation and Blinding

6.6.1 Participant Assignment

The patient decides after screening on its own if he wants to be operated or not. For this reason, the patient decides to which group he will belong.

6.6.2 Randomisation

There is no randomization

6.6.3 Blinding and Unblinding

There is no blinding

Emergency Unblinding: Because there is no blinding there is no need for emergency unblinding.

6.7 Trial Intervention Compliance

Trial compliance is only for the follow-up-evaluation. It does not concern the IMP, because the IMP is placed at the surgery in the patient. The compliance is expected to be high with the restrictions regarding activity and the compliance with the visits. It is expected that maximal 20% of patients will be lost for follow up or withdraw their consent.

6.8 Concomitant Therapy

There are no restrictions to concomitant therapy. There is no medication/supplement restriction for the trial. The IMP has no systemic effect. The patient can take all medications, which he has already, and which will be additionally during the trial period. There are only restrictions on activity as explained in 5.5.3 after surgery in the operated group.

6.8.1 Prohibited Concomitant Therapy

There is no prohibited concomitant therapy.

6.8.2 Permitted Concomitant Therapy

Every other therapy is permitted during the trial.

Rescue Therapy

There is no rescue therapy. The patient who progress to osteoarthritis or TKA would be excluded from data interpretation but would remain in the trial as the full analysis set principle is followed. This patient would be counted as failed treatment.

A withdrawal from the trial by the patient (after surgery) will only affect the follow-up data. Withdrawal before surgery will not generate follow-up data, but patient will still be left in the study due to the full analysis set principle. This does not lead to temporary discontinuation of the study.

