3 TRIAL OBJECTIVES, ENDPOINTS AND ESTIMANDS

3.1 Primary Objective + Associated Endpoint and Estimand

| Primary Objective | Primary Endpoint |
|---------------------------------------|--|
| To evaluate efficacy of the procedure | Improvement of PROMs (KOOS, IKDC, VAS Pain Score) 2 and 5 years after surgery compared to scores of the non-operated group and compared to pre-surgery scores. |

Primary Estimand (Variable): Difference in PROMs after 2 and 5 years

Endpoint: 2 and 5 years after surgery/enrollment, or progression to TKA

Treatment: varies with the group chosen by the patient (operated or not operated)

Population: male and female patients between 18 and 60 years

Intercurrent event: progression of osteoarthritis up to TKA, lost to follow up, premature death, the patient wishes to change to the operated group after a certain time (The process: progression of osteoarthritis is very slow. It will be very unlikely that more than 1 patient wants to change to the operated group within the 5 years of the trial. The same is true for progression to TKA. The possibility to change later in the operated group will take off the pressure from the patient to make the “wrong” decision now.)

Population-level summary: The primary objective is to compare the PROM change from baseline between the operated and non-operated group after 2 and 5 years. The difference in obtained PROMS will be evaluated.

Estimand Description: The Estimand are the Difference in PROMs. This includes specific knee scores (IKDC, KOOS) and the VAS-Pain Score. IKDC and KOOS have values between 0 and 100 and the higher they are as better the function of the knee. The VAS Pain Score has values between 0 and 10 and the higher the score the higher the pain.

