4.2 Rationale for Trial Design

Rationale for Intervention Model

The comparison of the 2 groups (operated/non-operated) are chosen, because this gives an instant possibility to compare the knee functionality with and without surgical treatment.

Rationale for Duration

Only after 2 years the result can be evaluated. Biological processes in the meniscus are slow. Shrinkage of the transplant as described for CMI can occur later (up to 2 years). But normally after 2 years the remodelling process is finished. For this reason, close follow-up is performed for up to 2 years.

Rationale for Endpoints

The endpoints are the knee functionality after 2 and 5 years, the safety of the patient and the efficacy of the method. If the benefit-risk balance changes the investigator evaluates if the study will be continued.

Progression of osteoarthritis up to TKA are additional end points for single participants.

Interim Analysis

An interim analysis will be performed in 2 years. If the benefit-risk balance changes or the safety of the patient or the efficacy of the procedure is not any more given, the study will be stopped.

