7 DISCONTINUATION OF TRIAL INTERVENTION AND PARTICIPANT WITHDRAWAL FROM TRIAL

7.1 Discontinuation of Trial Intervention

7.1.1 Criteria for Permanent Discontinuation of Trial Intervention

This is an orthopedic trial. The surgery is the start point and after the surgery there is no further treatment. There are only follow-up visits, which include an MRI (after 6 weeks, 6, 12, 24 months and 5 years in the operated group and after 24 months and 5 years in the non-operated group) and 3 questionnaires (IKDC and KOOS, CRF).

Criteria for permanent discontinuation for **single patients** from the trial are the following:

- Withdrawal of the informed consent
- lost to follow-up,
- premature death
- progression of osteoarthritis up to TKA
- the patient wishes to change to the operated group after a certain time

When withdrawal of the informed consent, premature death or lost to follow-up occurs, data up to the point will be used. If progression of osteoarthritis up to TKA occurs, the treatment is counted as treatment failure. These patients cannot continue the trial. Data up to the point will be used.

If the patient changes his decision and want to be operated at a later time point, the patient can continue the trial, but will be allocated to the other study arm. Data collected up to this point will be used in the first treatment group and then data will be generated in the second treatment group.

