9.2.2 Handling of Intercurrent Events of Primary Estimand(s)

Intercurrent events are: progression of osteoarthritis up to TKA, lost to follow up, premature death, the patient wishes to change to the operated group after a certain time. (as stated under point 3).

Data obtained until the event will be included in the analysis, last observation will be included in the evaluation. In case of progression of osteoarthritis up to TKA the procedure will be noted as fail. Premature death will be treated as lost to follow-up. Lost to follow-up and premature death can be unrelated to knee problems. If the patient wishes to change the treatment group, data are collected for this treatment up to the last treatment. If more than 20 % of patients fail, the benefit-risk balance will be re-evaluated, and it will be decided if the trial will be continued.

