9.2.3 Handling of Missing Data

If the patient withdraws his consent, data up to this date will be used for the analysis. The last observation carried out will be the end point. Patient will be reported as withdrawn.

Patients are not randomized and do not have therapy after surgery, they just have follow-up visits. There will be the full analysis set model for the analysis, thus all data from patients will be reported, which were

enrolled. If a patient is lost to follow up, the patient will be reported as this.

For patients with progressing of osteoarthritis up to TKA, they will be recorded as failed. Data up to the event will be analyzed.

There will be no assumptions made for missing data. Data from last observation will be analysed. A drop-out of 20% is accepted in orthopedic trials.

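### The Rescue Therapy paragraph excludes patients who progress to TKA from data interpretation, while 7.1.1, 9.2.2 and 9.2.3 use their data up to the event; the expected effect is small, but one rule is needed

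*Protocol*

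**What the plan says.** **Patients who progress to TKA.** The unnumbered Rescue Therapy paragraph, between 6.8.2 and 6.8.4, states: "The patient who progress to osteoarthritis or TKA would be excluded from data interpretation but would remain in the trial". It appeals to the full analysis set principle and counts the patient as a failed treatment. Section 7.1.1 says of patients with progression up to TKA: "These patients cannot continue the trial. Data up to the point will be used". Section 9.2.2, on intercurrent events of the primary estimand, says: "Data obtained until the event will be included in the analysis, last observation will be included in the evaluation". Section 9.2.3 records these patients as failed and analyses their data up to the event.

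**Patients who switch to surgery.** Section 7.1.1 lists the wish to switch among the criteria for permanent discontinuation from the trial. It then lets the patient continue after changing groups: "Data collected up to this point will be used in the first treatment group and then data will be generated in the second treatment group". Section 9.2.1 plans a two-sided t-test for independent groups, or a Mann-Whitney U test.

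**Missing data.** Section 9.2.3 says: "There will be no assumptions made for missing data. Data from last observation will be analysed". Section 9.2.4 states that a 20% dropout is acceptable and does not bias the result.

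**The concern.** The primary objective compares mean PROM change between groups. Whether a TKA patient's earlier scores belong in those means is part of the definition of the comparison, and the protocol answers it in two incompatible ways. Following 6.8.2 drops exactly those patients whom the protocol calls failures.

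The trial has no randomisation and no blinding. The investigator is also the sponsor, performs the analysis (9.7) and sees the outcome data while the trial is running. With two rules on paper, the choice between them could be made after the data are known.

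The event is also named differently. The Rescue Therapy paragraph joins osteoarthritis and TKA with an 'or', while the analysis sections speak of osteoarthritis progressing as far as TKA. Read literally, the paragraph covers a wider group.

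**Working it through.** **Step 1. The rules side by side.**

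| Section | Earlier PROM data of a TKA patient | Stays in the trial? |
|---|---|---|
| 6.8.2, Rescue Therapy | patient excluded from interpretation | yes |
| 7.1.1 | used up to TKA | no |
| 9.2.2 | used, with the last observation | not stated |
| 9.2.3 | analysed up to the event, recorded as failed | not stated |

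**Step 2. Expected number.** Section 11.1 allows 2.5% incomplete data from progression to TKA: 0.025 × 40 = 1 patient.

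**Step 3. One operated TKA patient.** Gains from 9.8: IKDC 84 - 55 = 29; KOOS 86 - 46 = 40. Let G be the mean gain of the other operated patients and g the last pre-TKA gain. The protocol does not give g, so it is assumed. The mean is G if the patient is excluded and ((n - 1)G + g)/n if included. The difference is (G - g)/n.

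| g | IKDC, n = 30 | KOOS, n = 30 | IKDC, n = 24 | KOOS, n = 24 |
|---|---|---|---|---|
| G | 0 | 0 | 0 | 0 |
| G/2 | 14.5/30 = 0.48 | 20/30 = 0.67 | 0.60 | 0.83 |
| 0 | 29/30 = 0.97 | 40/30 = 1.33 | 1.21 | 1.67 |
| -10 | 39/30 = 1.30 | 50/30 = 1.67 | 1.62 | 2.08 |

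The columns for n = 24 use the protocol's own 20% loss to follow-up.

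**Step 4. One control TKA patient.** Assume a last change d between 0 and -20, with the other controls unchanged on average. Excluding the patient raises the control mean by |d|/n: 0 to 20/10 = 2.0 points with 10 controls, and 0 to 20/8 = 2.5 with 8.

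**Step 5. Direction.** Excluding an operated patient with a below-average gain favours surgery. Excluding a control who worsened works against it. Section 12.1 expects more progression to TKA in the non-operated group.

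**Step 6. More exclusions.** As an illustration only, suppose six of 30 operated patients (20%) were excluded as failures, each with zero gain. Exclusion would then raise the mean by 6 × 29/30 = 5.8 IKDC or 6 × 40/30 = 8.0 KOOS points. The protocol does not forecast this number of TKAs.

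**Step 7. Power.** The stated figures reproduce with a two-sided noncentral t at effect size 2.0: 0.9935 for 10/30 at alpha 0.00655 (stated 0.993) and 0.9857 for 8/24 at alpha 0.014 (stated 0.985). Removing one operated patient from 8/24 gives 0.984; removing one control gives 0.974. Power is not the issue.

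**Step 8. One switcher in both groups.** With correlation r between that patient's two change scores, the variance of the mean difference is σ²(1/n₁ + 1/n₂ - 2r/(n₁n₂)). At 10/30 and r = 0.8 the bracket is 0.1333 - 0.0053 = 0.1280, about 4% less than the t-test assumes. In 100,000 simulated null trials at nominal 0.05, with r = -0.5, 0, 0.5 and 0.8, the type I error was 0.053, 0.050, 0.046 and 0.046 at 10/30, and 0.053, 0.050, 0.046 and 0.045 at 8/24.

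**Step 9. Missing data.** Using an earlier score as the 2-year or 5-year value assumes that the score would not have changed, so the two sentences quoted from 9.2.3 contradict each other. Whether dropout biases a comparison depends on who drops out, not only on how many do. Section 9.2.4 says only that loss can be unrelated to the knee, and gives no support for the absence of bias at 20%.

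**The case against.** The strongest reply is that almost nothing turns on this. The protocol expects about one TKA and at most one switch in five years. A TKA after year 2 does not affect the 2-year analysis. Three sections agree, so the Rescue Therapy sentence can be read as a slip. TKA by group is already planned, with Kaplan-Meier curves and a log-rank test (3.3, 9.1, 9.4), and other detail may sit in an SAP that is not shown.

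The point about size stands. The contradiction remains, because an SAP cannot follow two protocol rules at once. Reading the sentence as excluding only post-TKA data does not fit, since it excludes the patient. Counting the patient as failed does not settle it either, since a failure count supplies no value for a comparison of means.

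Several stronger readings are tempting, and the documents do not support them:

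- **Osteoarthritis short of TKA.** A reader might infer that the 'or' would remove many patients with poor results. It is probably loose wording. Section 2.1 itself reports cartilage damage on MRI alongside excellent function, so such patients need not have poor gains.
- **The meaning of endpoint.** A reader might take "Endpoint: 2 and 5 years after surgery/enrollment, or progression to TKA" in 3.1 to leave the outcome undefined. TKA is separately a secondary and an exploratory endpoint, and "Progression of osteoarthritis up to TKA are additional end points for single participants" in 4.2 follows the list of outcomes, so it does not clearly mean end of observation. In 9.2.3, "The last observation carried out will be the end point" concerns withdrawal of consent; the general rule is the later sentence on missing data.
- **Switchers.** A reader might infer that their later data have no home, or that double use invalidates the test. Section 7.1.1 does say where the data go, and Step 8 shows a negligible effect.

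**Conclusion.** The protocol fixes two incompatible rules for TKA patients in the primary PROM comparison, and this should be corrected. At the protocol's own expectation of one TKA, the shift is 0 to 1.3 IKDC or 0 to 1.7 KOOS points in the operated mean, or 0 to 2.0 points in the control mean, against the 20-point target in 9.2.1. These ranges rest on assumed last scores, on the planned gains in 9.8 and on full groups of 30 and 10.

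A reader might infer that the trial's conclusion would be overturned, or that the conflict always flatters surgery. Neither follows: the shift is small beside the target and its sign depends on the group. It would grow if more patients were excluded as failures.

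The claims in 9.2.3 and 9.2.4 that no assumption is made and that 20% dropout causes no bias are wrong as written. The switcher wording contradicts itself, with little numerical consequence.

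**What to change.** 1. In the Rescue Therapy paragraph, delete the clause excluding the patient from data interpretation. State there the rule of 7.1.1, 9.2.2 and 9.2.3: every enrolled patient stays in the full analysis set, and PROM data up to TKA are included. Show the already planned TKA counts by group beside the PROM result.
2. Name the event throughout as the other sections do: progression of osteoarthritis up to TKA.
3. Let a switcher count once in the primary PROM test, with the data from the other group listed separately.
4. In 9.2.3, say that analysing the last observation is an assumption, and add one sensitivity analysis on observed data. In 9.2.4, delete the statement that 20% dropout does not bias the result.
5. Reconcile the Rescue Therapy paragraph with 7.1.1 on whether TKA patients remain in follow-up, and the two statements in 7.1.1 on switchers. This review takes no position on which is right.

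Worst-rank scoring of TKA and reassignment of switchers can be left to the SAP. The cost is wording and one small extra analysis on 40 patients. Results may move slightly in either direction.
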